### 5.3 Packaging, Labeling and Storage

The IMP, Viaskin® patch (active and placebo), is manufactured until primary packaging stage (patch in pouch) by CCI [REDACTED]. Each pouch will be labeled and packaged by CCI [REDACTED] in accordance with Good Manufacturing Practices and applicable local regulatory requirements. The labeled treatment boxes will be dispensed to subjects at each visit, with enough quantity of Viaskin® patches to cover the period between 2 consecutive visits.

The labeled and packaged IMP must be stored in accordance with the Sponsor's instructions (below 25°C [77°F] and should not be frozen). Shipments from depots to clinical sites will be performed at refrigerated temperature between 2°C to 8°C [36°F to 46 F] with a temperature monitoring device.

Upon receipt of a shipment request via IWRS, the IMP will be shipped to the clinical site. The site pharmacist or any other staff member designated for this task will receive and store the IMP until the time of dispensing. Until dispensed by the Investigator to the subjects, the IMP will be stored in a securely locked area, accessible to authorized personnel only. At the end of the study, or at times designated by the Sponsor, and after complete accountability, the site pharmacist or the designated person will be responsible for preparing the return of the used (partially) and unused IMP to the IMP distributor. Destruction of IMP on-site is not allowed.

### 5.4 Blinding and Breaking the Blind

The study will be performed in a double-blind manner. Active and placebo DBV712 patches will be supplied in identical pouches and will be similar in physical appearance, thereby enabling double-blind conditions.

The treatment codes will be integrated to the IWRS. Investigators have the possibility to unblind a treatment via the IWRS in some specific cases (as detailed below). Further instructions for emergency code break will be provided in a separate IWRS User Guide.

The study blind should not be broken except in a medical emergency (where knowledge of the IMP received would affect the treatment of the emergency) or due to a regulatory requirement (for example for Suspected Unexpected Serious Adverse Reactions

[SUSAR]). The blind will only be broken at the discretion of the Investigator. All unblinding events will be recorded and reported by the IWRS to the Medical Monitor and the Sponsor. In case of IWRS failure, a backup system is operated 24 hours every day of the year enabling unblinding of treatment by calling the IWRS hot line (Please refer to IWRS User Guide).

If the blind is broken, the date, time, and reason must be recorded in the subject's source documents, in the electronic Case Report Form (e-CRF) and any associated AE must be reported.

If a subject (parents/guardians), is unblinded, this must be listed as major protocol deviation and the concerned subject(s) will be withdrawn from the study.

Serious unexpected suspected adverse reactions, which are subject to expedited reporting, will be unblinded before submission to the Regulatory Authorities.

The overall randomization code will be broken only for data analyses of study Part A or Part B, as follows:

- Part A data will be unblinded when the last subject from Part A will have completed the study, and
- Part B data will be unblinded when the last subject from Part B will have completed the study.

Unblinding will be performed when all final clinical data have been entered into the database and all data queries have been resolved, the e-CRF has been signed and locked, and the assignment of subjects to the analysis populations has been completed.

### 5.5 Drug Accountability

The Investigator is responsible for maintaining accurate IMP accountability records throughout the study. Each site will have to complete a site IMP accountability log and an individual IMP accountability log for each subject. These records should include the amounts and dates that IMP supplies were received on-site, dispensed to the subject, returned by the subject, and returned to IMP distributor (or destroyed on-site, if applicable).

Each dispensing of IMP will be performed via IWRS.

### 5.6 Compliance

It is the Investigators' responsibility to ensure that subjects' parents/guardians are correctly instructed on how to store and administer the IMP. Records of IMP used and intervals between visits will be kept during the study. Drug accountability will be monitored by CRO site monitor during site monitoring visits and at the completion of the study. Subjects' parents/guardians will be asked to return their unused IMP (boxes and patches) when they come back for their study visits. All unused IMP (boxes and patches) should be returned to the IMP distributor. The IMP should be dispensed by the Investigator, or by a qualified individual under the Investigator's supervision. An up-to-date drug accountability record must be maintained (see Section 5.5).

At each visit, prior to dispensing the IMP, previously dispensed IMP will be retrieved by the Investigator and compliance assessed. Compliance at each visit is to be calculated

taking into account the total number of patches applied since the last visit *versus* the number of days in that period of time. Subjects exhibiting poor compliance (below 80%) at any specific time point during the treatment period should be counseled on the importance of good compliance to the study dosing regimen.

Subjects who are persistently non-compliant will be withdrawn from the study (see Section 4.3).

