### 4.3 Patient Withdrawal and Replacement

#### 4.3.1 Subjects Stopping Rules

Subjects must be withdrawn from the study treatment under the following circumstances:

- Severe anaphylaxis (stage 3 anaphylaxis, see [APPENDIX 4](#)) related to Viaskin® patch application (either peanut or placebo patch);
- More than 2 intramuscular epinephrine injections for an AE related to Viaskin® patch application (either peanut or placebo patch), and not occurring during the DBPCFC nor related to an accidental food allergen consumption.

Subjects may be required to be withdrawn from the study treatment or study after discussion with the Investigator and/or Sponsor for the following reasons:

- AE(s);
- Severe “maculo-papular rash” or severe generalized atopic “dermatitis” outside of patch application area, which failed to be controlled by adequate corrective treatments (including topical corticosteroids) and in spite of several study treatment interruptions;
- At the discretion of the Investigator, if she/he decides that it is in the subject’s best interest to be withdrawn from the study;
- The subject is unwilling to continue in the study (consent withdrawal);
- Lack of compliance with protocol requirements and procedures;
- The subject fails to return to the clinic for scheduled visits and does not respond to telephone or written attempts at contact (lost to follow-up);

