#### ***4.3.4 Data Collection and Follow-up after Withdrawal***

If a subject is prematurely withdrawn from the IMP for any reason before completing all study visits, the Investigator must make every effort to perform the evaluations described for the Early Termination Visit (see Section 7.2.12). The Investigator must furthermore complete all appropriate subject diary and e-CRF pages, providing the date and explanation for the subject’s withdrawal/discontinuation. When indicated, the Investigator must

arrange for appropriate follow-up and/or alternative medical care of the discontinued subject.

If the subject fails to attend a scheduled End of Study Visit, there will be at least two documented attempts to contact the subject's parents/guardians via telephone and written communication. If no reply is received, the subject will be considered as lost to follow-up.

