#### *7.2.12 Early Termination Visit*

Subjects who discontinue early from the study should have, if possible, an Early Termination Visit. This visit should take place as soon as possible after the subject stops applying the IMP).

The following assessments will be performed at these visits:

- Physical examination (including a complete skin examination; see Section 6.2.4);
- Vital signs (see Section 6.2.3);
- SPT (see Section 6.4.2);
- Immunological markers (see Section 6.4.1);
- Laboratory tests (Section 6.2.2);

- US eligible sites only: collect blood sample for BAT (see Section 6.4.7);
- AEs recording (including volunteered or solicited AEs and AESI);
- Concomitant medications (see Section 5.7);
- Check for any accidental peanut consumption (see Section 6.4.4);
- Check subject diary;
- Check unused medication and assess medication compliance;
- Patch adhesion Investigator's assessment: made with the patch still applied, the Investigator assesses the adherence of the patch to the skin as well as the occlusion of the patch chamber. This assessment will only be made if the subject is wearing the patch at the time of the visit. Any issues reported by the subjects' parents/guardians related to the patches application or removal will also be reported;
- Check skin reactions and grade severity (see Table 3, Section 6.2.6);
- Take a photograph of the sites of application of the Viaskin® patch, load it onto the study server (described in Section 6.2.6) and keep it in the subject's medical records or source documents; download the photographs taken by the parents' subject from the camera memory card or the device, if any photos were taken since the previous visit and review them.

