**Table 3 - Intercurrent Event Types**

Label	Intercurrent Event Type	Comment (for main estimand)
Intercurrent event 1 (Early treatment Discontinuation before 12 Months*)	Treatment exposure < M12 and missing peanut DBPCFC	Subjects will be included in the FAS. Subjects will be considered as a non-responder.
Intercurrent event 2 (subject/caregiver refusing the Month 12 peanut DBPCFC)	Treatment exposure $\geq$ M12, subject had not started the peanut DBPCFC and refusing to ingest the peanut formula	Subjects will be included in the FAS. An imputation will be used for missing data.
Intercurrent event 3 (peanut DBPCFC initiated but not finished)	Child starting the DBPCFC and stopped without symptoms leading to ending the peanut DBPCFC (stopping rules) (e.g. refusing to ingest the peanut formula left due to fear, aversion)	Subjects will be included in the FAS. An imputation will be used for missing data.
Intercurrent event 4 (peanut DBPCFC completed at Month 12* falls outside the recommended time-window)	Delayed peanut DBPCFC completed at Month 12 (e.g. due to temporarily closed centers or postponed visits (COVID-19))	Subjects will be included in the FAS. Actual values will be used regardless of whether an intercurrent event has occurred.
Intercurrent event 5 (discontinuation at or after Month 12 * with Month 12 peanut DBPCFC missing)	Treatment exposure $\geq$ M12 but missing peanut DBPCFC (e.g. due to temporarily closed centers or postponed visits (COVID-19))	Subjects will be included in the FAS. An imputation will be used for missing data.

\*Month 12 time windows are comprised between 358 – 407 days (section 5.2.7).

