**Table 4 - Primary endpoint and Estimand with Rationale for Strategies to Address Intercurrent Events**

Estimand description	
Treatment efficacy will be evaluated using the difference between the percentage of treatment responders in the selected active DBV712 (250 µg) group compared to the placebo group after 12 months of treatment in the target population.
 
A combination of strategies will be used to treat separately the different intercurrent events.

Target Population	Pediatric subjects aged 1 to 3 years, with diagnosed peanut allergy or high suspicion of peanut allergy, enrolled and randomized following confirmation of all eligibility criteria
Analysis Set	Full Analysis Set
Variable/Endpoint	
A subject is defined as a treatment responder:
 
 
• If the screening ED was ≤10 mg peanut protein and the ED is ≥ 300 mg peanut protein at the post-treatment DBPCFC at Month 12,
 
 
OR
 
 
• If the screening ED was >10 mg peanut protein and the ED is ≥ 1,000 mg peanut protein at the post-treatment DBPCFC at Month 12.
 

Treatment Condition(s)	DBV712 250 µg group or placebo (Reference: Placebo).
Population-Level Summary	Difference in treatment responder rates between DBV712 250µg and placebo.
Intercurrent Event Strategy	
Intercurrent event 1	Composite strategy (subjects considered as non-responders)
Intercurrent event 2	Composite strategy (subjects will mimic placebo response)
Intercurrent event 3	Composite strategy (mBOCF)
Intercurrent event 4	Treatment policy
Intercurrent event 5	Composite strategy (subjects will mimic placebo response)
Rationale for Strategy(s)	
Composite strategy is used for intercurrent events 1, 2, 3 and 5 as follows:
 
 
- Early treatment discontinuations before 12 Months (Intercurrent event 1) are considered as non-responders
 

CONFIDENTIEL / Ne pas diffuser sans autorisation de DBV

CONFIDENTIAL / Do not distribute without DBV authorization

	Statistical Analysis Plan	
	EPITOPE (V712-304) – Statistical Analysis Plan	
	Référence du Document /Document Reference : CCI	Page : 37 / 74

CCI

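### Protocol 5.6 makes study withdrawal mandatory for persistent non-compliance where 4.3.1 leaves it discretionary, so a Month 12 challenge that might have been observed is lost (cheap improvement, low priority)

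*Protocol*

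**What the plan says.** **Compliance rule.** Protocol Section 5.6 calculates compliance at each visit from patches applied against days elapsed, and asks for counselling when it is below 80% at any time point. It then ends: "Subjects who are persistently non-compliant will be withdrawn from the study (see Section 4.3". It does not define what counts as persistent.

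**The section it cites.** Section 4.3.1 has two lists. The mandatory list holds two patch-related safety events (stage 3 anaphylaxis, and more than two epinephrine injections) and requires withdrawal from treatment only. The second list opens "Subjects may be required to be withdrawn from the study treatment or study after discussion with the Investigator and/or Sponsor for the following reasons", and one of its entries is "Lack of compliance with protocol requirements and procedures".

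**What happens afterwards.** For a child taken off the patch prematurely, Section 4.3.4 says that "the Investigator must make every effort to perform the evaluations described for the Early Termination Visit (see Section 7.2.12". Section 7.2.12 adds: "Subjects who discontinue early from the study should have, if possible, an Early Termination Visit". The assessments listed there do not include a DBPCFC. Under Section 6.1.1 and the Schedule of Procedures, the challenge is done only at entry and at Month 12 (Visits 10 and 11).

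**Scoring.** Protocol Section 8.5.1.1 counts a missing Month 12 eliciting dose as non-response in the ITT population. SAP Table 3 defines intercurrent event 1 as "Treatment exposure < M12 and missing peanut DBPCFC", keeps the child in the FAS and scores non-response. Step 3 of the method in SAP Table 4 carries this out.

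**The concern.** Section 5.6 changes its own cross-reference in two ways: a discretionary step becomes mandatory, and a choice between leaving treatment and leaving the study becomes leaving the study. Two sites following the protocol could handle the same child differently.

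The statistical consequence is avoidable missing data on the primary endpoint. The primary analysis covers all randomised children, whatever their compliance, so a poor complier's Month 12 challenge is a result the analysis wants. Removing the child from the study discards a result that might have been observed and replaces it with an assigned failure. The SAP's sensitivity analyses score event 1 as failure, impute it from placebo or exclude it. None can restore the challenge result.

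**Working it through.** **1. The chain, link by link.** Persistent non-compliance leads to withdrawal from the study (5.6). Withdrawal leads to an Early Termination Visit without a challenge (4.3.4, 7.2.12). No challenge and exposure below Month 12 lead to event 1, scored non-responder (8.5.1.1; SAP Tables 3 and 4). The limit to before Month 12 matters. With exposure of at least Month 12 and no challenge, event 5 applies and the response is imputed from placebo.

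**2. Reproduce the plan's figure.** Inputs from the Synopsis (Number of Subjects, Part B): 233 active and 117 placebo; response 40% and 10%, with missing already counted as failure for up to 15% drop-out; success if the lower bound of the two-sided 95% Newcombe interval is at least 15 points.

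- Lower bound: d − √[(p₁ − l₁)² + (u₂ − p₂)²], where d = p₁ − p₂, l₁ is the lower Wilson limit for active and u₂ the upper Wilson limit for placebo.
- Power: the sum of the two binomial probabilities over all outcomes that meet the criterion.
- Result: 90.8%. The stated 350 subjects for at least 90% reproduces.

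**3. Illustrate the effect.** The documents give no withdrawal share, so I assume that an extra w = 5% of both arms is affected beyond the drop-out allowance (0.05 × 233 ≈ 12 active, 0.05 × 117 ≈ 6 placebo).

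- Withdrawn, scored failures: active 0.40 × 0.95 = 38.0%, placebo 0.10 × 0.95 = 9.5%, difference 28.5 points.
- Kept, all attend: active 0.40 × 0.95 + 0.05 × r, where r is the response rate of the active low compliers. Placebo stays at 10%.

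| Case (w = 5%) | Active | Placebo | Power | Change against withdrawn |
|---|---|---|---|---|
| Withdrawn | 38.0% | 9.5% | 85.2% | – |
| Kept, r = 40% | 40.0% | 10.0% | 90.8% | +5.7 |
| Kept, r = 20% | 39.0% | 10.0% | 86.9% | +1.7 |
| Kept, r = 10% | 38.5% | 10.0% | 84.5% | −0.7 |

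Changes are in percentage points, from unrounded power. The two policies break even at r = 12.8%. Below that, keeping the children slightly lowers power, because kept placebo children also respond at times. If only half attend and the rest are failures, power is 88.3%, 86.0% or 84.8%.

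At w = 2%, power is 88.8% if withdrawn, and 90.8%, 89.4% or 88.6% if kept.

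**4. Check with the SAP's interval.** The Farrington-Manning score test at 15 points with w = 5% gives 91.5% for the plan, 86.3% if withdrawn, and 91.5%, 87.8% or 85.5% if kept. The pattern is the same.

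**The case against.** The case for leaving the text alone is fair in several respects. Section 5.6 sends the reader to 4.3, where discussion and a choice are provided, so a site could reconcile the two. Scoring early discontinuation as failure is a deliberate pre-specified strategy, and the sample size already allows for it. Protocol Section 1.3 reports very good compliance in earlier studies, though in older children. Families who do not apply patches may not attend a two-day challenge. A change needs an amendment across 51 sites in 8 countries (SAP 3.1.1), and SAP 5.2.3 already describes randomisation in the past tense. These points stand. They limit the priority, but they do not make the two sections agree or supply the missing result.

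A reader might also infer four stronger things that the documents do not support:

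- **That the below-80% categories contradict 5.6.** They do not. Section 5.6 counsels below 80% and withdraws only persistent cases, so low compliers can stay under it. Withdrawn children also remain in the populations from which the PP set (Protocol 8.1.1.3) and the compliance table (SAP 5.3.8) are drawn.
- **That the SAP is unclear about an early stopper who does have a challenge.** The event 1 label, "Early treatment Discontinuation before 12 Months", and the Table 4 sentence "Early treatment discontinuations before 12 Months (Intercurrent event 1) are considered as non-responders" are loosely worded. But Table 3 requires a missing challenge, SAP 5.2.4 and Step 3 of Table 4 act on missing values, and SAP 5.2.7 uses the Visit 10 or 11 challenge regardless of window.
- **That failure scoring can never favour the active arm.** It also lowers the placebo rate. With 5% withdrawn in placebo only (40% against 9.5%), power rises to 92.9%. Nothing in the documents suggests such an imbalance.
- **That the rule biases the comparison or surely costs power.** No difference between arms is shown, and the table above has changes of both signs.

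**Conclusion.** The point holds as a cheap improvement of low priority. Read as written, Section 5.6 goes further than the section it cites and discards a primary outcome that may have been observable. The reason to change it is that observed data are better than assigned failures in an all-randomised analysis. A gain in power is not assured.

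The size cannot be fixed from the documents. Inside the 15% drop-out allowance there is no cost against plan. Beyond it, at an assumed 5% in both arms, keeping the children moves power by between +5.7 and −0.7 points. That range rests on response rates of 40% down to 10% in active low compliers, 10% in placebo, and full attendance. The sample size is not in question.

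**What to change.** - **Protocol 5.6:** replace the last sentence with: *Low compliance alone does not end study participation; whether patch treatment continues is decided under 4.3.1.*
- **Protocol 4.3.4:** state that such a child keeps the scheduled visits, including the Month 12 DBPCFC (Visits 10 and 11), unless consent is withdrawn or the challenge is medically contraindicated. At present 4.3.4 does not say whether those visits still take place for a child who only stops the patch.
- **SAP Tables 3 and 4 (optional):** one line saying that event 1 applies only when the Month 12 peanut challenge is missing. This clarifies what Table 3 already says and is not a needed correction. If added, it should be in place before unblinding.

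**Cost.** A protocol wording amendment, with the approvals that Section 9.10 requires. No new procedure is added, since Visits 10 and 11 are already scheduled. Some children with low exposure would undergo a challenge up to 2,000 mg with its reaction risk, as placebo children already do, and some families may not attend. The change can help only children who have not yet been withdrawn.

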## 5.7 Prior and Concomitant Medication

Any medication taken by the subject other than the IMP, including herbal and other non-traditional remedies, is considered as concomitant medication. Any medication used in the last 6 months or being administered at the time of screening is considered as prior medication.

At screening, children parents or guardians will be asked what medications the child has been taking during the last 6 months. At each subsequent study visit, children parents or guardians will be asked what concomitant medications the child is currently taking. All concomitant and prior medications must be recorded in the e-CRF.

The following information must be recorded in the e-CRF for each prior and concomitant medication: generic name, route of administration, start date, stop date, dosage, total daily dose, and indication. Any changes in the dosage or regimen of a concomitant medication must be recorded in the e-CRF.

Of note, prior or concomitant medication prescribed to a subject but not actually taken or administered should not be reported in the e-CRF, such as the epinephrine auto-injector prescribed for use in case of anaphylaxis but never injected intramuscularly.

### 5.7.1 Permitted Concomitant Medication

Application of a topical corticosteroid to treat any local condition (eczematous lesions, pruritus, edema, etc.) is permitted.

For local reactions to the Viaskin® patch, a topical medication (ointment, gel, cream) with 0.5% to 1% hydrocortisone or equivalent will be distributed to each randomized subject at discharge on Day 1. In case the 1% hydrocortisone topical medication is not sufficient to treat the local reaction, a topical medication containing a more potent corticosteroid can be prescribed and locally applied in accordance to the local approved indication of each product for the subject age class.

Oral antihistamines or oral corticosteroids are allowed to treat conditions determined as being allergic reactions and should be recorded as concomitant medications. These treatments should be limited in duration and stopped as soon as the condition has resolved. The Investigator will determine the best choice of treatment, the dose and the regimen according to the subject's age, and the type and the degree of severity of the reactions. Cetirizine is recommended as the oral antihistamine of choice.

Oral antihistamines or oral corticosteroids must be washed out for the minimum period of time prior to the skin prick testing or to the food challenges (see Section 5.7.2 for detail on wash-out periods).

Intramuscularly injectable epinephrine (auto-injector EpiPen® or any other trade name available at the right dosage in the different countries) will be distributed to each parent or

guardian at discharge on Day 1 to be used in case of symptoms of anaphylaxis. The Investigator will explain to the parents/guardians when and how to inject the epinephrine according to the Anaphylaxis Emergency Action Plan. The intramuscularly injectable epinephrine will be replaced if used or if it expires. Any use of injectable epinephrine should be recorded as a concomitant medication.

All other treatments prescribed by the Investigator or any other physician to treat any conditions are also permitted. Medications that are not noted in the Section 5.7.2 are also permitted.

